4.7.4.9 Sustained MBS Freedom from 2 to 24 Hours

Sustained MBS freedom is assessed using the number of mITT subjects that experienced freedom from their MBS at all time points from 2 through 24 hours post-dose. Subjects with missing MBS scores at 1 or fewer time points, given that they have responses of freedom from

MBS at all other time points including the 2 and 24 hour post-dose time points will be considered as successes. Subjects with responses missing at greater than 1 post-dose time point, missing data at the 2 or 24 hour time point, or with any report of presence of MBS will be considered as failures.

The results to be presented for the analysis include those described in items (a) through (e) for the primary analysis of pain freedom ([Section 4.7.3.1](#)). In this case, the “risk” is the probability of sustained MBS freedom from 2 to 24 hours.

4.7.4.10 Sustained MBS Freedom from 2 to 48 Hours

Sustained MBS freedom is assessed using the number of mITT subjects that experienced freedom from their MBS at all time points from 2 through 48 hours post-dose. Subjects with missing MBS scores at 1 or fewer time points, given that they have responses of freedom from MBS at all other time points including the 2, 24, and 48 hour post-dose time points will be considered as successes. Subjects with responses missing at greater than 1 post-dose time point, missing data at the 2, 24, or 48 hour time point, or with any report of presence of MBS will be considered as failures.

The results to be presented for the analysis include those described in items (a) through (e) for the primary analysis of pain freedom ([Section 4.7.3.1](#)). In this case, the “risk” is the probability of sustained MBS freedom from 2 to 48 hours.

4.7.4.11 Sustained Normal Functioning from 2 to 24 Hours

Sustained normal functioning is assessed using the number of mITT subjects that experienced normal functioning on the FDS at all time points from 2 through 24 hours post-dose. Subjects with missing FDS scores at 1 or fewer time points, given that they have responses of normal at all other time points including the 2 and 24 hour post-dose time points will be considered as successes. Subjects with responses missing at greater than 1 post-dose time point, missing data at the 2 or 24 hour time point, or with any report of non-normal functioning will be considered as failures.

The results to be presented for the analysis include those described in items (a) through (e) for the primary analysis of pain freedom ([Section 4.7.3.1](#)). In this case, the “risk” is the probability of sustained normal functioning from 2 to 24 hours.

4.7.4.12 Sustained Normal Functioning from 2 to 48 Hours

Sustained normal functioning is assessed using the number of mITT subjects that experienced normal functioning on the FDS at all time points from 2 through 48 hours post-dose. Subjects with missing FDS scores at 1 or fewer time points, given that they have responses of normal at all other time points including the 2, 24, and 48 hour post-dose time points will be considered as successes. Subjects with responses missing at greater than 1 post-dose time point, missing data at the 2, 24, or 48 hour time point, or with any report of non-normal functioning will be considered as failures.

The results to be presented for the analysis include those described in items (a) through (e) for the primary analysis of pain freedom (Section 4.7.3.1). In this case, the “risk” is the probability of sustained normal functioning from 2 to 48 hours.

4.7.4.13 Pain Freedom at 90 Minutes

Pain freedom at 90 minutes post-dose is assessed by tabulating the number of mITT subjects that report a pain level of none (response of 0 on the 4-point Likert scale) at 90 minutes post-dose, by treatment group. Subjects with missing data at 90 minutes post-dose will be imputed as failures (NC=F).

The results to be presented for the analysis include those described in items (a) through (e) for the primary analysis of pain freedom (Section 4.7.3.1). In this case, the “risk” is the probability of pain freedom at 90 minutes post-dose.

4.7.4.14 MBS Freedom at 90 Minutes

MBS freedom at 90 minutes post-dose is assessed by tabulating the number of mITT subjects that report an absence of their MBS at 90 minutes post-dose, by treatment group. Subjects with missing data at 90 minutes post-dose will be imputed as failures (NC=F).

The results to be presented for the analysis include those described in items (a) through (e) for the primary analysis of pain freedom (Section 4.7.3.1). In this case, the “risk” is the probability of MBS freedom at 90 minutes post-dose.

4.7.4.15 Pain Relapse from 2 to 48 Hours

Pain relapse is assessed using the number of mITT subjects that are pain free at 2 hours post-dose as the denominator. The numerator is the number of these subjects that then have a relapse of pain at any severity (response of 1, 2, or 3 on the 4-point Likert scale) within 48 hours after administration of study medication. Subjects with more than 1 time point with missing data or with missing data at the 2, 24, or 48 hour time point are classified as relapsers.

The results to be presented for the analysis include those described in items (a) through (e) for the primary analysis of pain freedom (Section 4.7.3.1). In this case, the “risk” is the probability of sustained pain relapse from 2 to 48 hours.

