2.3.2 Secondary Estimands

The estimands corresponding to the secondary objectives are shown in [Table 2](#).

The population summary for all secondary estimands is the difference in the percentage of subjects with a positive result (‘risk difference’) between the BHV-3000 and the Placebo treatment groups.

Table 2: Estimands for the Secondary Objectives

Objective	Pain Relief (at 60 minutes, 90 minutes, or 2 hours)
Population	mITT
Variable	Percent of subjects who report mild or no pain at the specified timepoint
Intercurrent Events	NC=F; RM=F
Objective	Functional Disability (at 60 minutes, 90 minutes, or 2 hours)
Population	mITT
Variable	Percent of subjects with a response of “normal” at the specified timepoint
Intercurrent Events	NC=F; RM=F
Objective	Sustained Pain Relief (2 to 24 hours; or 2 to 48 hours)
Population	mITT
Variable	Percent of subjects who report no pain or mild pain during the period of interest
Intercurrent Events	NC1=F; RM=F
Objective	Sustained Freedom from MBS (2 to 24 hours; or 2 to 48 hours)
Population	mITT
Variable	Percent of subjects who report freedom from MBS during the period of interest
Intercurrent Events	NC1=F; RM=F
Objective	Probability of Rescue Medication within 24 hours post-dose
Population	mITT
Variable	Percent of subjects taking rescue medication within 24 hours post-dose
Intercurrent Events	None
Objective	Sustained Normal Functioning (2 to 24 hours; or 2 to 48 hours)
Population	mITT
Variable	Percent of subjects who report normal functioning on the FDS during the period of interest
Intercurrent Events	NC1=F; RM=F
Objective	Photophobia Freedom at 2 hours post-dose
Population	mITT subjects with photophobia reported as present at migraine onset
Variable	Percent of subjects reporting no photophobia at 2 hours post-dose
Intercurrent Events	NC=F; RM=F
Objective	Sustained Pain Freedom (2 to 24 hours; or 2 to 48 hours)
Population	mITT
Variable	Percent of subjects who report no pain during the period of interest
Intercurrent Events	NC1=F; RM=F
Objective	MBS Freedom at 90 minutes post-dose
Population	mITT subjects
Variable	Percent of subjects reporting freedom from MBS at 90 minutes post-dose
Intercurrent Events	NC=F; RM=F
Objective	Pain Freedom at 90 minutes post-dose
Population	mITT
Variable	Percent of subjects who report no pain at 90 minutes post-dose
Intercurrent Events	NC=F; RM=F
Objective	Phonophobia Freedom at 2 hours post-dose
Population	mITT subjects with phonophobia reported as present at migraine onset

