Variable	Percent of subjects reporting no phonophobia at 2 hours post-dose
Intercurrent Events	NC=F; RM=F

Objective	Nausea Freedom at 2 hours post-dose
Population	mITT subjects with nausea reported as present at migraine onset
Variable	Percent of subjects reporting no nausea at 2 hours post-dose
Intercurrent Events	NC=F; RM=F

Objective	Pain Relapse (2 to 48 hours)
Population	mITT subjects who report pain freedom at 2 hours post-dose
Variable	Percent of subjects who report any pain during the period of interest
Intercurrent Events	NC1=F; RM=F

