4.2.5 Multiple Comparisons

Type I error is controlled in this study by using a hierarchical gate-keeping procedure. First, the family of two co-primary endpoints is tested. If the co-primary endpoints are both found to be significant, then secondary endpoints are tested in a fixed sequence. In particular, each co-primary endpoint will be tested for superiority to placebo at a two-sided alpha level of 0.05 without further adjustment for multiplicity. If the primary endpoint tests are both significant, then the following secondary endpoints will be tested in a fixed sequence, in the order shown, with each test conducted at $p=0.05$:

1. Pain Relief at 2 hours
2. Functional Disability at 2 hours
3. Sustained Pain Relief from 2 to 24 hours
4. Sustained Freedom from MBS from 2 to 24 hours
5. Probability of Rescue Medication within 24 hours
6. Sustained Normal Functioning (on FDS) from 2 to 24 hours
7. Sustained Pain Relief from 2 to 48 hours
8. Sustained Freedom from MBS from 2 to 48 hours
9. Sustained Normal Functioning (on FDS) from 2 to 48 hours
10. Freedom from Photophobia at 2 hours

11. Functional Disability at 90 minutes
12. Pain Relief at 90 minutes
13. Sustained Pain Freedom from 2 to 24 hours
14. MBS Freedom at 90 minutes
15. Pain Freedom at 90 minutes
16. Freedom from Phonophobia at 2 hours
17. Sustained Pain Freedom from 2 to 48 hours
18. Pain Relief at 60 minutes
19. Functional Disability at 60 minutes
20. Freedom from Nausea at 2 hours
21. Pain Relapse from 2 to 48 hours

If a test in the hierarchy is not significant, then any further tests on endpoints in the sequence will have p-values presented only for descriptive purposes, and no conclusions will be drawn from those results.

For exploratory endpoints, no attempt will be made to adjust for multiplicity. Any exploratory endpoints for which p-values are produced will be evaluated at an unadjusted two-sided alpha level of 0.05 and presented only for descriptive purposes.

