4.7.4.6 Sustained Pain Freedom from 2 to 48 Hours

Sustained pain freedom is assessed using the number of mITT subjects that experienced no headache pain (response of 0 on Likert scale) at all time points from 2 through 48 hours post-dose. Subjects with missing pain scores at no more than 1 time point, given that they have responses of no pain (response of 0 on Likert scale) at the 2, 24, and 48 hour time points will be considered as successes. Subjects with responses missing at greater than 1 time point; missing data at the 2, 24, or 48 hour time point; or with any pain score greater than 0 will be considered as failures.

The results to be presented for the analysis include those described in items (a) through (e) for the primary analysis of pain freedom ([Section 4.7.3.1](#)). In this case, the “risk” is the probability of sustained pain freedom from 2 to 48 hours.

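### Does testing pain relapse only among subjects who are pain free at 2 hours call for a caveat, bounds or a change of status in the SAP?

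*SAP*

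**What the plan says.** SAP section 4.7.4.15 sets the denominator: "Pain relapse is assessed using the number of mITT subjects that are pain free at 2 hours post-dose as the denominator". Table 2 in section 2.3.2 gives the same population for the estimand, "mITT subjects who report pain freedom at 2 hours post-dose", and the text above the table fixes the summary measure: "The population summary for all secondary estimands is the difference in the percentage of subjects with a positive result". Protocol section 3.2, endpoint 21, describes relapse in the same way.

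Section 4.2.5 places the test: "If the co-primary endpoints are both found to be significant, then secondary endpoints are tested in a fixed sequence", each at 0.05, with "21. Pain Relapse from 2 to 48 hours" as the final entry. Two related endpoints come before it, "13. Sustained Pain Freedom from 2 to 24 hours" and "17. Sustained Pain Freedom from 2 to 48 hours", and both are analysed in all mITT subjects. For the second of them, section 4.7.4.6 says that subjects with "missing data at the 2, 24, or 48 hour time point; or with any pain score greater than 0 will be considered as failures". Section 4.7.4.15 treats missing data in the matching way, as relapse, and Table 2 lists the same intercurrent-event rules for both endpoints.

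Neither section 2.3.2, 4.2.5, 4.7.4.15 nor Appendix 3 comments on the conditioning or plans a sensitivity analysis for it. The only further relapse table (14.2.2.16.2) excludes Site 002.

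**The concern.** Randomisation protects a comparison of all treated subjects. It does not protect a comparison of those who happened to be pain free at 2 hours. If rimegepant works, its responders include people who would also have responded to placebo and people who responded only because of the drug. The placebo responders contain no one of the second kind. If the two kinds relapse at different rates, the relapse proportions differ even when the drug does nothing to relapse.

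The sequence sharpens the point, because #21 is formally tested only after 2-hour pain freedom has been shown to differ. Beyond the mITT definition itself, #21 is also the only secondary endpoint restricted by a post-dose outcome; the photophobia, phonophobia and nausea endpoints condition on symptoms at migraine onset. At stake is a significant #21 being reported, with confirmatory standing, as evidence that the drug prevents relapse.

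**Working it through.** **Planned figures.** SAP section 4.1: 0.85 × 715 = 607.75, stated as about 600 per arm; 0.95 × 0.95 = 0.9025, stated as roughly 90% joint power. Both reproduce. No rate, size or power is given for #21, and the rates from studies 301 and 302 behind the 95% are not stated.

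**Link to #17.** With matching missing-data and rescue rules, the relapse proportion is essentially 1 − (#17 successes ÷ subjects pain free at 2 hours).

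**What selection alone can do.** Let p1 and p0 be the pain-free proportions on rimegepant and placebo, r0 the placebo relapse proportion, and s = p0/p1. Assume nobody is pain free on placebo who would not be on rimegepant. With no drug effect on relapse, the rimegepant relapse proportion must lie between s·r0 and s·r0 + (1 − s).

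**Simulation.** Assumed inputs: 600 per arm, r0 of 30%, 40% or 50%, drug-only responders relapsing 10 or 20 points less or more than the others, and no drug effect on relapse. Test: unstratified, unpooled Wald, two-sided 0.05, with 2-hour pain freedom and #17 both required to be significant first. There were 1,000,000 runs per scenario. The table shows the probability of passing both earlier tests and rejecting on #21.

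| Drug-only responders | Direction counted | 20% vs 12% pain free (assumed, near planned power) | 31.4% vs 15.3% (Phase 2b) |
|---|---|---|---|
| relapse 10 points less | favours rimegepant | 7.8–8.0% | 12.7–13.7% |
| relapse 20 points less | favours rimegepant | 18.7–21.5% | 37.0–44.6% |
| relapse 10 points more | favours placebo | 0.4–3.4% | 9.3–14.6% |
| relapse 20 points more | favours placebo | 0.5–6.2% | 19.8–39.0% |
| relapse equally | both | 2.8–3.7% | 4.9–5.3% |

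The nominal level is 2.5% per direction. The other earlier tests were not modelled and could only lower these figures. In the scenarios with a gap, rejection in the direction not shown was 0.7% or less.

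**A borderline result.** Take 20% vs 12% pain free, so 600 × 0.20 = 120 and 600 × 0.12 = 72 responders, and r0 = 40%. A rimegepant relapse rate of 26% is just significant: SE = √(0.26 × 0.74/120 + 0.40 × 0.60/72) = 0.0703, z = 0.14/0.0703 = 1.99. With s = 0.60, the selection-only range is 0.60 × 0.40 = 24% to 24% + 40% = 64%, so 26% falls inside it. Reaching 26% by selection requires 0.60 × 0.40 + 0.40 × x = 0.26, so x = 5%: drug-only responders relapsing at 5% against 40%, a 35-point gap. Gaps of 10 and 20 points give expected rates of 36% and 32%.

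**The only data in the documents.** Protocol section 1.3.2 gives Phase 2b pain freedom of 31.4% vs 15.3% at 2 hours and sustained pain freedom from 2 to 24 hours of 27.9% vs 7.4%. Assuming a common denominator within each arm:

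- Loss of pain freedom: 1 − 27.9/31.4 = 11.1% on rimegepant; 1 − 7.4/15.3 = 51.6% on placebo.
- s = 15.3/31.4 = 0.487. Selection-only floor: 0.487 × 51.6% = 25.2%. The observed 11.1% is below it.
- Bounds on drug for subjects pain free on either treatment: max(0, (0.111 − 0.513)/0.487) = 0 to 0.111/0.487 = 22.9%, against 51.6%. The difference is −51.6 to −28.8 points.

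These are 24-hour point estimates with sampling error ignored.

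**The case for a change.** The strongest case for acting is that #13 and #17 do not answer the question #21 seems to ask. They can be significant simply because more subjects became pain free on rimegepant; they do not show that responders relapse less because of the drug. The SAP limits interpretation elsewhere, for exploratory p-values and after a failed test, and is silent here. A few sentences and a small table would cost little.

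The logic stands; the gain from writing it into the SAP does not. The estimand already states its conditional population, and neither document says that #21 isolates a drug effect. Each possible remedy also falls short:

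- **A caveat** records a reading that the stated denominator already implies. It changes no planned result.
- **Bounds** need only four proportions, which planned tables 14.2.1.1.2 and 14.2.2.16.1 supply; only their confidence intervals need further work. They rest on the untestable assumption that nobody is harmed, and the simple formula ignores the stratified analysis. In the borderline example they run from 0 to 0.26/0.60 = 43%, against 40% on placebo, which says almost nothing.
- **Resting durability claims on #13 and #17 alone** would wrongly leave out the sustained pain relief, MBS freedom and normal functioning endpoints (#3, #4, #6, #7, #8, #9), which also use all mITT subjects and are tested earlier.
- **Removing #21 from the sequence** is a debatable trade-off. It frees no alpha for another test and departs from the order set by Protocol sections 2.2 and 9.4.2.

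**Conclusion.** No change to the plan follows. The SAP compares relapse in groups formed after randomisation, and a significant #21 should not be read by itself as a drug effect on relapse. The test is nevertheless valid for the estimand stated, is the last of 21, passes on no alpha, and is reached only after both co-primaries and all 20 earlier secondaries succeed. The consequence is limited to the wording of one result in the study report, where a statistician can describe it as a comparison among 2-hour responders and set it beside #17.

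The simulated rejection rates illustrate what selection could do. They depend on assumed relapse rates, an assumed gap between responder types, nobody being harmed, and a reduced set of earlier tests. The documents give no 2–48 hour relapse rates and no support for either direction of the gap; if drug-only responders relapse more, selection works against rimegepant. An effect as large as the Phase 2b point estimates suggest would keep its sign under the bounds, while at smaller differences the bounds can include zero.

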4.7.5 Exploratory Efficacy Endpoints

Any p-values presented for exploratory efficacy endpoints are for descriptive purposes only.

4.7.5.1 Functional Disability Scale at 24 Hours

Data will be analyzed in the same manner as described in Section 4.7.4.4. However, in this case the analysis will use the data from the 24 hour post-dose time point.

4.7.5.2 *Pain Relief at 15, 30, 60 and 90 Minutes Post-Dose*

Pain relief at 15, 30, 60, and 90 minutes post-dose will be assessed by tabulating the number of mITT subjects that report a pain level of none or mild (responses of 0 or 1 on the 4-point Likert scale) at the specified post-dose time point by treatment group. Subjects with missing data at the specified post-dose time point will be imputed as failures (NC=F).

First, the data will be evaluated at each time point for each time point, using the first analysis methods described in [Section 4.7.3.1](#).

Pain relief over time up to 8 hours will be analyzed using Kaplan-Meier methods. Kaplan-Meier estimates will be tabulated using the following time periods (0 through 15 minutes, >15 through 30 minutes, > 30 through 60 minutes, > 60 through 90 minutes, > 90 through 120 minutes, >120 minutes through 180 minutes, >180 minutes though 240 minutes, >240 minutes though 360 minutes, >360 minutes though 495 minutes, and > 495 minutes). For each time period, the number of subjects at risk, with an event (pain freedom), censored, and survival probability estimate (with 95% CI), will be presented by treatment group. Subjects who fail to reach no pain by 495 minutes, will be censored at 496 minutes. Additionally, subjects who take rescue medication prior to 495 minutes will be censored at the date/time associated with their rescue medication. Note that the probability of survival corresponds to the probability of NOT having pain relief. Survival estimates are calculated using the Kaplan-Meier product-limit method and median survival (time to pain freedom), and will be presented along with 95% CIs calculated using the method of Brookmeyer and Crowley.

To support the analysis, a Kaplan-Meier plot, with time in minutes on the x-axis and probability of survival on the y-axis, will be presented by treatment group. The number at risk at each time point (0, 15, 30, 45, 60, 90, 120, 180, 240, 360, and 495) minutes will be presented below the figure. In this analysis, being at risk corresponds to not yet having achieved pain relief; therefore, the subject is still “at risk” of having pain freedom. Once a subject has pain relief or is censored, then the subject is no longer in the risk pool. If a subject has missing data at an earlier time point, then the time point with missing data is not considered. The subject is still considered at risk of failure at a future time point if data are available. Subjects are censored as described above.

4.7.5.3 *Preference of Medication (PoM)*

The PoM is a brief scale that captures the subjects’ perception of whether the medication they are taking has had a greater benefit compared with previous medications to treat their pain. Responses at 24 hours post-dose for all subjects who provided a response, and answered “yes” to the lead-in question (i.e. “Have you ever taken migraine medication”), will be tabulated. The number and percentage of subjects preferring the study medication, along with 95% asymptotic CIs, are presented by treatment group. The tabulations will be repeated for the subset of subjects considered as responders or non-responders by treatment group without imputation, where responders are those subjects who reported a pain score of 0 or 1 at 2 hours post-dose and who did not require rescue medication at or prior to 2 hours post-dose.

4.7.5.4 *Migraine Quality of Life Questionnaire (MQoLQ)*

Impact of treatment on patient-reported quality of life is assessed using the MQoLQ, which is a 15-item instrument that has been validated in migraine patients to measure the short-term impact of treatment (within 24 hours). The MQoLQ consists of 15 items across the following five domains: (1) work functioning, (2) social functioning, (3) energy/vitality, (4) migraine symptoms, and (5) feelings/concerns. There are three items within each domain. Response options for each of the items are on a 7-point scale where 1 indicates maximum impairment of QoL and 7 indicates no impairment. Each domain has a maximum score of 21 and a minimum score of 3. The items in the work functioning domain are: (1) ability to do normal everyday work, (2) ability to operate machinery or a motor vehicle, and (3) ability to stay alert. The items in the social functioning domain are: (1) interactions with people who are close to you, (2) interactions with other people, and (3) ability to enjoy life. The items in the energy/vitality domain are: (1) energy level, (2) ability to have a good night's sleep, and (3) mood. The items in the migraine symptoms domain are: (1) have throbbing head pain, (2) have increased sensitivity to light and/or noise, and (3) have nausea. Lastly, the items in the feelings/concerns domain are: (1) feel upset about having migraine headaches, (2) feel physically uncomfortable, and (3) feel concern that your migraine medication wouldn't relieve your migraine headache symptoms.

The observed responses at 24 hours post-dose will be presented for each item, each domain, and as a total score, by treatment group. The observed responses at 24 hours will also be summarized as a continuous response for each item, domain, and for the total score. Responses will also be presented in a by-subject listing along with treatment group, historical MBS collected at screening, MBS reported at migraine onset, migraine severity just prior to study medication, and migraine severity at 24 hours post-dose.

4.7.5.5 *Efficacy at Each Pose-Dose Time Point*

Pain freedom, pain relief, freedom from MBS, and functional disability score will be tabulated by treatment group at each post-dose time point. Success for each of these endpoints will be tabulated using the mITT subjects.

Freedom from nausea, freedom from phonophobia, freedom from photophobia, and FDS response will be tabulated by treatment group at each post-dose time point. The tabulation will include: the total number of subjects reporting each of the above symptoms at baseline, success as the percentage of the total number of subjects reporting the symptoms at baseline, and the number of subjects that reported the symptom but with missing data at the post-dose time point as a percentage of the number reporting the symptom at baseline.

4.7.5.6 *Pain Freedom to 8 Hours Post-Dose*

Pain freedom over time up to 8 hours will be analyzed using Kaplan-Meier methods. Kaplan-Meier estimates will be tabulated using the following time periods (0 through 15 minutes, >15 through 30 minutes, > 30 through 60 minutes, > 60 through 90 minutes, > 90 through 120 minutes, >120 minutes through 180 minutes, >180 minutes though 240 minutes, >240 minutes though 360 minutes, >360 minutes though 495 minutes, and > 495 minutes). For each time period, the number of subjects at risk, with an event (pain freedom), censored, and survival

probability estimate (with 95% CI), will be presented by treatment group. Subjects who fail to reach no pain by 495 minutes, will be censored at 496 minutes. Additionally, subjects who take rescue medication prior to 495 minutes will be censored at the date/time associated with their rescue medication. Note that the probability of survival corresponds to the probability of NOT having pain freedom. Survival estimates are calculated using the Kaplan-Meier product-limit method and median survival (time to pain freedom), and will be presented along with 95% CIs calculated using the method of Brookmeyer and Crowley.

To support the analysis, a Kaplan-Meier plot, with time in minutes on the x-axis and probability of survival on the y-axis, will be presented by treatment group. The number at risk at each time point (0, 15, 30, 45, 60, 90, 120, 180, 240, 360, and 495) minutes will be presented below the figure. In this analysis, being at risk corresponds to not yet having achieved pain freedom; therefore, the subject is still “at risk” of having pain freedom. Once a subject has pain freedom or is censored, then the subject is no longer in the risk pool. If a subject has missing data at an earlier time point, then the time point with missing data is not considered. The subject is still considered at risk of failure at a future time point if data are available. Subjects are censored as described above.

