14.2.2.12.3	Sustained MBS Freedom from 2 to 24 Hours Post Dose: Secondary Analysis Excluding Site 002	mITT Subjects Excluding Site 002	

Table Number	Title	Population	Topline
14.2.2.12.4	Sustained MBS Freedom from 2 to 48 Hours Post Dose: Secondary Analysis Excluding Site 002	mITT Subjects Excluding Site 002	
14.2.2.13.1	Sustained Normal Functioning from 2 to 24 Hours Post Dose: Secondary Analysis	mITT Subjects	Y
14.2.2.13.2	Sustained Normal Functioning from 2 to 48 Hours Post Dose: Secondary Analysis	mITT Subjects	Y
14.2.2.13.3	Sustained Normal Functioning from 2 to 24 Hours Post Dose: Secondary Analysis Excluding Site 002	mITT Subjects Excluding Site 002	
14.2.2.13.4	Sustained Normal Functioning from 2 to 48 Hours Post Dose: Secondary Analysis Excluding Site 002	mITT Subjects Excluding Site 002	
14.2.2.14.1	Pain Freedom at 90 Minutes Post Dose: Secondary Analysis	mITT Subjects	Y
14.2.2.14.2	Pain Freedom at 90 Minutes Post Dose: Secondary Analysis Excluding Site 002	mITT Subjects Excluding Site 002	
14.2.2.15.1	Freedom from Most Bothersome Symptom at 90 Minutes Post Dose: Secondary Analysis	mITT Subjects	Y
14.2.2.15.2	Freedom from Most Bothersome Symptom at 90 Minutes Post Dose: Secondary Analysis Excluding Site 002	mITT Subjects Excluding Site 002	
14.2.2.16.1	Pain Relapse from 2 to 48 Hours Post Dose: Secondary Analysis	mITT Subjects	Y
14.2.2.16.2	Pain Relapse from 2 to 48 Hours Post Dose: Secondary Analysis Excluding Site 002	mITT Subjects Excluding Site 002	
14.2.3.1	Functional Disability Scale at 24 Hours Post Dose: Exploratory Analysis	mITT Subjects	
14.2.3.2	Pain Relief at 15 and 30 Minutes Post Dose: Exploratory Analysis	mITT Subjects	
14.2.3.3.1	Kaplan-Meier Time to First Report of Pain Relief up to 8 Hours Post Dose: Exploratory Analysis	mITT Subjects	Y
14.2.3.3.2	Median Time to First Report of Pain Relief: Exploratory Analysis	mITT Subjects	Y
14.2.3.4	Preference of Medication at 24 Hours Post Dose: Exploratory Analysis	mITT Subjects	Y
14.2.3.5.1	Migraine Quality of Life Questionnaire at 24 Hours Post Dose: Continuous Exploratory Analysis	mITT Subjects	
14.2.3.5.2	Migraine Quality of Life Questionnaire at 24 Hours Post Dose: Frequency Exploratory Analysis	mITT Subjects	
14.2.3.6	Pain Freedom at Every Timepoint Post Dose: Exploratory Analysis	mITT Subjects	Y
14.2.3.7	Pain Relief at Every Timepoint Post Dose: Exploratory Analysis	mITT Subjects	Y

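### SAP 4.7.5.2 names pain freedom as the event of its pain-relief Kaplan-Meier analysis, against its own survival definition, exit rule and output titles

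*SAP*

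**What the plan says.** SAP section 4.7.5.2 covers pain relief, defined there as a score of 0 or 1 on the 4-point scale. Its second part introduces a Kaplan-Meier analysis of relief over 8 hours. Three of its operative statements concern pain freedom instead:

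- Event: "For each time period, the number of subjects at risk, with an event (pain freedom), censored, and survival probability estimate".
- End of window: "Subjects who fail to reach no pain by 495 minutes, will be censored at 496 minutes".
- Median: "median survival (time to pain freedom".

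Three others concern relief:

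- Survival: "Note that the probability of survival corresponds to the probability of NOT having pain relief".
- Risk set: "being at risk corresponds to not yet having achieved pain relief".
- Exit: "Once a subject has pain relief or is censored, then the subject is no longer in the risk pool".

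The risk-set sentence is itself mixed. After defining risk by the absence of relief, it goes on to say that the subject remains at risk of pain freedom.

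In Appendix 1, Table 14.2.3.3.1 is titled "Kaplan-Meier Time to First Report of Pain Relief up to 8 Hours Post Dose: Exploratory Analysis" and Table 14.2.3.3.2 "Median Time to First Report of Pain Relief: Exploratory Analysis". Figure 14.2.8 also carries a relief title. All three are marked topline. Section 4.7.5.6 contains the same event, window and median wording for a separate pain-freedom analysis with its own outputs (Tables 14.2.3.13.1 and 14.2.3.13.2, Figure 14.2.9).

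On rescue medication, 4.7.5.2 and 4.7.5.6 both censor at the time of rescue. Section 4.7.1 treats rescue users as failures for every efficacy evaluation from rescue onwards.

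**The concern.** The event definition is the rule a programmer codes from, and here it disagrees with the definition of survival in the same analysis. If the event, window and median statements are followed, the topline relief outputs repeat the pain-freedom analysis of 4.7.5.6 under a relief title. If they are combined with the exit rule, some subjects have no defined outcome.

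There is also a smaller point of labelling. The per-timepoint topline tables (14.2.3.6 for freedom, 14.2.3.7 for relief) fall under the failure rule of 4.7.1, while the topline curves for the same outcomes censor at rescue. Nothing in the output titles tells the reader that the two displays treat rescue users differently.

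**Working it through.** **1. Can the rules be applied together?** Take four subjects who take no rescue medication and have complete diaries.

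| Course after dosing | Exit rule (relief) | Event and window text (freedom) |
|---|---|---|
| Moderate or severe, then none | Leaves at that time | Event at that time |
| Mild at 60 min, none at 3 h | Leaves at 60 min | Event at 3 h, when already out of the risk set |
| Mild at 60 min, never below mild | Leaves at 60 min, with no named event | Censored at 496 min |
| Never below moderate | Stays at risk | Censored at 496 min |

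The rules agree in the first and last rows. They conflict whenever the first response is mild pain. In the third row the subject leaves the risk set at 60 minutes with no named event and is also to be censored at 496 minutes.

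**2. How many subjects could this concern?** Inputs: the Phase 2b 2-hour rates in Protocol 1.3.2 (placebo, rimegepant), which are relief 51.2% and 72.1%, freedom 15.3% and 31.4%; and about 600 treated subjects per arm (SAP 4.1). The 2-hour status stands in for the first report by 2 hours.

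- Mild pain at 2 h = relief minus freedom.
- Placebo: 0.512 − 0.153 = 0.359; 0.359 × 600 = 215.
- Rimegepant: 0.721 − 0.314 = 0.407; 0.407 × 600 = 244.
- Difference between arms at 2 h: 0.721 − 0.512 = 20.9 points as relief; 0.314 − 0.153 = 16.1 points as freedom.
- Median: both relief rates exceed 50%, so the relief median falls at or before 2 h, though placebo clears 50% by only 1.2 points. Both freedom rates are below 50%, so the freedom median falls after 2 h if first reports track 2-hour status.

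Protocol 1.2.2.8 gives the placebo freedom rate once as 15.2%. With that value the placebo count is 0.360 × 600 = 216.

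**3. Does rescue censoring have a known effect on the treatment difference?** Let r be the 2-hour response rate, s the share of non-responders who take rescue just after 2 h, and q the chance of a later response by 8 h without rescue. The documents give neither s nor q.

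- Censored at rescue: 1 − (1 − r)(1 − q).
- Rescue as failure: r + (1 − r)(1 − s)q.
- The first exceeds the second by (1 − r)sq in each arm.

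For relief, with the same s in both arms, the treatment difference under rescue as failure minus the difference under censoring is s(0.488 q_placebo − 0.279 q_rimegepant). Assumed values give:

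| q placebo | q rimegepant | Bracket | s = 0.3 | s = 0.5 |
|---|---|---|---|---|
| 0.50 | 0.50 | 0.1045 | +3.1 points | +5.2 points |
| 0.40 | 0.70 | −0.0001 | 0 | 0 |
| 0.30 | 0.70 | −0.0489 | −1.5 points | −2.4 points |

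The sign depends on the assumptions, so neither size nor direction can be stated.

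**The case against.** The strongest reply is that this is carried-over wording and that the intent is plain. The section heading, the opening sentence of the analysis, the survival definition, the exit rule and all three output titles say relief, and pain freedom has its own section. That stands. It means that a wrong table is a risk and not a foregone outcome, and that the 215 and 244 subjects measure the gap between two readings, one of them unlikely. It does not remove the contradiction, because the event, the end-of-window criterion and the median are all stated as freedom.

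On rescue, the reply is also largely right. The censoring rule is explicit in both sections, and a specific rule for one analysis may stand beside a general one. Table 3 of the SAP covers the exploratory objectives, none of which is a time-to-event objective, so the lack of a row for these curves is not shown to be an omission. What remains is that the outputs do not say which rule they use.

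A reader might go further and infer that censoring at rescue biases the curves, or that it shrinks the treatment difference and so works against the drug. The documents do not support either. They give no rescue rates and no response rates after 2 hours, and the third step of the working shows the shift changing sign within plausible assumptions. Protocol 5.4.1 allows rescue for lack of relief at 2 hours or for recurrence, which makes it plausible that rescue is related to prognosis, but plausibility is not a demonstration.

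**Conclusion.** The contradiction is real and should be corrected. Three operative statements in 4.7.5.2, and part of its risk-set sentence, describe pain freedom in an analysis that is otherwise one of pain relief. The rules cannot be reconciled for a subject whose first response is mild pain, and at the Phase 2b rates that could concern more than a third of each arm (35.9% and 40.7%). Those percentages assume that the earlier study's 2-hour rates carry over and that 2-hour status approximates the first report.

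The consequence is limited. SAP 4.2.5 and 4.7.5 make exploratory p-values descriptive only, so no co-primary or secondary test is touched. The weight comes from the topline status of the outputs. The rescue point is one of labelling: the curves and the per-timepoint tables answer different questions, and the plan should say so.

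**What to change.** In SAP 4.7.5.2:

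- define the event as the first pain score of 0 or 1;
- apply the 496-minute censoring to subjects with no score of 0 or 1 by 495 minutes;
- describe the median as time to pain relief;
- change the end of the risk-set sentence so that the subject is at risk of pain relief.

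If the outputs have already been programmed, confirm which event was coded for Tables 14.2.3.3.1 and 14.2.3.3.2 and Figure 14.2.8.

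As a minor addition, label the curves and tables from 4.7.5.2 and 4.7.5.6 as censored at rescue. Optionally, add one display per curve that keeps rescue users in the risk set without an event to 496 minutes, in line with 4.7.1.

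The cost is a few wording changes and a footnote, plus one recoded censoring time and one extra display per curve if the option is taken. Sample size, alpha and the testing order are unchanged.
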